2. PARTICIPANTS

2.1. [DETERMINATION] Participants. Describe the general characteristics of the subject populations or groups, including age range, gender, health status, and any other relevant characteristics.

Document Date & Version

06.29.2023

Version 4.6

APPLICATION IRB Protocol

Researcher Date & Version

mm/dd/yyyy

Version x.x

Page 7 of 55

We plan to recruit adult patients who are admitted to UW Montlake, Harborview and Northwest hospitals with history of type 2 diabetes mellitus on insulin therapy prior to admission. Because we work with the internal medicine hospitalist group, these patients are admitted for various non-critical acute illnesses from the emergency room. They can also be non-emergent admissions from the clinics. The obstetrics ward tends to use a different glycemic goal than other inpatient populations, so we exclude patients admitted to obstetrics ward. Our prior observation cohort did not include patients admitted for elective surgery or procedure, so our calculator has not been validated in this population.

2.2. [DETERMINATION] Inclusion and exclusion criteria.

2.2.a. Inclusion criteria. Describe the specific criteria that will be used to decide who will be included in the research from among interested or potential subjects. Define any technical terms in lay language.

1. Patients who are admitted to University of Washington Medical Center – Montlake, Harborview and Northwest hospitals
2. Aged ≥ 18 years
3. With history of type 2 or steroid-induced diabetes mellitus
4. Receiving insulin therapy prior to admission

2.2.b. Exclusion criteria. Describe the specific criteria that will be used to decide which of the subjects who meet the inclusion criteria listed above will be excluded from the research. Define any technical terms in lay language.

1. Patients who are admitted to ICU or obstetrics ward
2. Patients who are admitted for elective surgery or procedure
3. Patients who present with diabetic ketone acidosis, hyperosmolar hyperglycemic state or need IV insulin infusion
4. Patients who have no meal intake for 24 hours prior to admission, planned nothing per oral (NPO) during the first 24 hours after admission
5. Patients who report low appetite (25% or less) on admission or have a significantly decreased level of consciousness that study team does not think they are going to eat right after admission
6. Patients who receive enteral feeding after admission

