2.4.d. If the research is funded by one of these federal departments and agencies (Health & Human Services; Energy; Defense; Homeland Security; CIA; Social Security Administration), and/or will involve prisoners in federal facilities or in state/local facilities outside of Washington State: check the box below to provide assurance that study team members will (a) not encourage or facilitate the use of a prisoner’s participation in the research to influence parole or pardon decisions, and (b) clearly inform each prisoner in advance (for example, in a consent form) that participation in the research will have no effect on his or her parole or pardon.

☐ **Confirmed**

2.5. [DETERMINATION] Protected populations. IRB approval is required for the use of the subject populations listed here. Check the boxes for any of these populations that will be purposefully included. (In other words, being a part of the populations is an inclusion criterion for the study.)

The WORKSHEETS describe the criteria for approval but do not need to be completed and should not be submitted.

Document Date & Version

06.29.2023

Version 4.6

APPLICATION IRB Protocol

Researcher Date & Version

mm/dd/yyyy

Version x.x

Page 9 of 55

Check all that apply	Population	Worksheet Name and Link
	Fetuses in utero	WORKSHEET Pregnant Women
	Neonates of uncertain viability	WORKSHEET Neonates
	Non-viable neonates	WORKSHEET Neonates
	Pregnant women	WORKSHEET Pregnant Women

2.5.a. If you check any of the boxes above, use this space to provide any information that may be relevant for the IRB to consider.

Click or tap here to enter text.

2.6. [DETERMINATION] Native Americans or non-U.S. indigenous populations. Will Native American or non-U.S. indigenous populations be actively recruited through a tribe, tribe-focused organization, or similar community-based organization?

Indigenous people are defined in international or national legislation as having a set of specific rights based on their historical ties to a particular territory and their cultural or historical distinctiveness from other populations that are often politically dominant.

Examples: a reservation school or health clinic; recruiting during a tribal community gathering.

☒ **No**

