Our UW observational cohort (STUDY00015475) has 1/140 patients (0.7%) who had hypoglycemia < 54 mg/dL during the first 24 hours of hospitalization. We think 3% increase (which means 3.7%) is considered clinically significant increase, so among these 85 subjects there cannot be more than $85 \times 3.7\% = 3.15$ subjects that develop hypoglycemia < 54 mg/dL. So, if we find more than 3.15 patients (round to 4) who develop BG < 54 during the recruitment, that is more than 3% increase. Because this is the first feasibility trial to apply the calculator on patients, we plan to enroll 10 subjects first, to demonstrate the calculator dose does not cause hypoglycemia (≤ 54 mg/dL). After these 10 participants are recruited, we will review and analyze these data. Then we will apply for a modification to increase the sample size.

UW inpatient insulin order set comes with hypoglycemia protocols which will be used to manage hypoglycemia if it occurs.

If hospitalists do not feel comfortable with the calculator doses when they enroll subjects, they will contact PI: [name] in real time, and we will double-check the calculator doses. If these subjects are admitted after midnight and PI: [name] is unavailable for discussion, hospitalists will not enroll the subject. Hospitalists and PI: [name] will then discuss this scenario (subject not enrolled) to understand the reasons hospitalists did not feel comfortable with the calculator dose.

10.2. [DETERMINATION] Reproductive risks. Are there any risks of the study procedures to subjects or partner of subjects related to pregnancy, fertility, lactation or effects on a fetus or neonate?

Examples: direct teratogenic effects; possible germline effects; effects on fertility; effects on a woman's ability to continue a pregnancy; effects on future pregnancies.

☒ **No** → Go to [question 10.3.](#)

☐ **Yes** → Answer the following questions:

10.2.a. Risks. Describe the magnitude, probability, duration and/or reversibility of the risks.

Click or tap here to enter text.

10.2.b. Steps to minimize risk. Describe the specific steps that will be taken to minimize the magnitude, probability or duration of these risks.

Examples: inform the subjects about the risks and how to minimize them; require a pregnancy test before and during the study; require subjects to use contraception; advise subjects about banking of sperm and ova.

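### Exclusion 1 works by ward only, so a patient known to be pregnant on a medicine ward is eligible as written; sections 2.1, 2.2.b and 10.2 should be reconciled (minor)

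*Combined protocol and SAP*

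**What the plan says.** Section 2.1 gives the reason for the obstetrics exclusion: "The obstetrics ward tends to use a different glycemic goal than other inpatient populations, so we exclude patients admitted to obstetrics ward". Exclusion 1 in section 2.2.b puts it into effect: "Patients who are admitted to ICU or obstetrics ward".

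The inclusion criteria in 2.2.a require admission to one of the three named hospitals, "Aged ≥ 18 years", "With history of type 2 or steroid-induced diabetes mellitus" and "Receiving insulin therapy prior to admission". None of them limits sex or pregnancy status.

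On where subjects come from, section 2.1 says: "Because we work with the internal medicine hospitalist group, these patients are admitted for various non-critical acute illnesses from the emergency room". It adds that non-emergent admissions from clinics are possible.

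Section 10.2 asks whether the study procedures carry risks "related to pregnancy, fertility, lactation or effects on a fetus or neonate". The box ticked is No, and no reasoning is given.

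**The concern.** The exclusion identifies patients by bed, while recruitment takes place in a service where few, if any, patients are in an obstetrics bed. In the stream actually being screened, the obstetrics part of exclusion 1 therefore removes few pregnant patients or none. Section 1.5 names one glycemic goal, 100-180 mg/dL, and lists the calculator's inputs; pregnancy is not among them.

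What is at stake is patient safety and a clear eligibility rule, in a feasibility trial whose main question is safety and which is the first to apply the calculator to patients. The No in 10.2 is easy to follow if pregnant patients cannot enter. The criteria do not ensure that, and if such patients can enter, the plan does not explain the answer.

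**Working it through.** This is a check of wording, and the plan has no figure of its own to reproduce.

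**Step 1. Run one hypothetical patient through section 2.2.** Take an adult known to be pregnant, with type 2 diabetes on home insulin, eating normally, admitted to a medicine ward at one of the three hospitals.

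| Criterion | Result |
|---|---|
| Inclusion 1, hospital | met |
| Inclusion 2, age | met |
| Inclusion 3, diabetes type | met |
| Inclusion 4, prior insulin | met |
| Exclusion 1, ICU or obstetrics ward | not triggered (medicine ward) |
| Exclusion 2, elective surgery or procedure | not triggered |
| Exclusion 3, ketoacidosis, hyperosmolar state or IV insulin | not triggered |
| Exclusions 4 to 6, oral intake, consciousness, enteral feeding | not triggered |
| Exclusion 7, kidney injury needing dialysis | not triggered |

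Result: eligible as written. Gestational diabetes alone would not satisfy inclusion 3, so the gap is narrow.

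**Step 2. Look for a rule elsewhere that closes the gap.**

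- Section 5.1 repeats the exclusions on appetite, fasting and consciousness. It does not mention pregnancy.
- Section 5.4 lists the calculator inputs and the data to be extracted. Pregnancy status is in neither list.
- Section 10.8 gives the withdrawal rules. None concerns pregnancy.
- Section 2.5 leaves the box for pregnant women unticked. The form explains that a tick means "being a part of the populations is an inclusion criterion for the study". An unticked box therefore says that pregnant women are not targeted; it does not exclude them.

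Nothing in the visible text closes the gap.

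**Step 3. Set 10.2 beside 10.1.** Section 10.1 accepts that the calculator dose carries a possible risk of hypoglycemia, and notes that usual care carries it too. Section 10.2 answers No to pregnancy-related and fetal risk. Both can be true if no pregnant patient can enter, or if the sponsor has reasons to see no added risk. The first is not secured by 2.2.b, and the second is not stated.

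**Step 4. Size.** The expected number of such subjects is 85 × p, where p is the share of otherwise eligible admissions that are pregnant. The documents do not give p. Purely as an assumed range:

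- p near 0: about 0 of 85
- p = 0.5%: 85 × 0.005 = 0.4
- p = 2%: 85 × 0.02 = 1.7

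Nothing in the documents supports any of these values over the others, including the lowest. For mean BG, one subject in 85 carries a weight of 1/85 = 1.2%, so the mean would move by 1.2% of that subject's difference from the rest, which is negligible.

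**The case against.** The best case on the other side is that 2.1 and 2.2.b agree. Section 2.1 describes what the obstetrics ward tends to do, and exclusion 1 names the same ward. A reader might infer that the plan breaks its own rule, because the reason belongs to pregnancy and not to the bed. The documents do not support that. Nowhere do they say that a pregnant patient on a medicine ward is managed to another goal. This part of the objection stands, so the point is a gap in coverage and not a contradiction.

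A reader might also infer that such a subject would be scored against an unsuitable target. That does not hold either. The 100-180 mg/dL goal is not an endpoint. The endpoints are BG below 54 mg/dL, mean BG over the first 24 hours, and BG of 300 mg/dL or more. The first and last are fixed thresholds that do not depend on any ward's goal.

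A third inference is that one such subject could tip the safety limit (85 × 3.7% = 3.15, rounded to 4 in section 5.1). That is true of every subject, and nothing in the documents shows a higher hypoglycemia risk with the calculator in pregnancy.

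It is also fair to say that:

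- The No in 10.2 is a judgment about risk, not about eligibility. Items 10.2.a to 10.2.c are blank because the form tells the applicant to skip them after a No.
- Safeguards limit the consequence. Only the initial dosing is set by the calculator, glucose is checked within 5-6 hours of that dose, the order set includes hypoglycemia protocols, and a hospitalist who is uneasy about a calculated dose contacts the PI.
- The consent pages are not in the available text and the monitoring plan was uploaded separately (10.6), so a statement on pregnancy there cannot be ruled out.

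These points reduce the importance of the gap but do not close it. The safeguards concern the dose and what follows it, not who may enter, and an eligibility rule belongs in section 2.2.

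**Conclusion.** The gap is real and minor. As written, a patient known to be pregnant who meets the diabetes and insulin criteria and is admitted to medicine can be enrolled, and the No in 10.2 is unexplained in that case. The sections fit together literally; the weakness is that the ward is used as a stand-in in a study that recruits elsewhere. The number of subjects affected is unknown and may be near zero of 85, and the effect on the endpoints is negligible. The case for a change rests on patient safety and clarity at almost no cost, not on any bias in the analysis. It assumes that the unseen consent and monitoring documents do not already settle the matter.

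**What to change.** Reconcile 2.1, 2.2.b and 10.2 in one of two ways.

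1. Extend exclusion 1 by adding, after the ward clause, *or known to be pregnant, on any ward*. Use pregnancy status already in the admission record, with no added test. Add a matching clause to the reason in 2.1. The No in 10.2 can then stand, with one sentence saying that it rests on this exclusion.
2. If the sponsor does intend such patients to be eligible, say so in 2.2 and give the reasoning for the answer in 10.2.

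The first option costs one phrase in 2.2.b and a sentence each in 2.1 and 10.2. Its downside is the loss of at most a very few eligible patients. The eligibility rules of the comparison cohort (STUDY00015475) on pregnancy are not shown, so the sponsor should check whether that cohort included pregnant patients and, if it did, note the difference.

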3. NON-UW RESEARCH SETTINGS

Complete this section only if UW investigators and people named in the SUPPLEMENT Non-UW Individual Investigators will conduct research procedures outside of UW and Harborview

- 3.1. [DETERMINATION] Research locations and rationale.** Identify the locations where the research will be conducted and include a description of the reason(s) for choosing the locations. If the research will be conducted internationally, be sure to list all the countries where the research will take place.

This is especially important when the research will occur in locations or with populations that may be vulnerable to exploitation. One of the three ethical principles the IRB must consider is Justice: ensuring that reasonable, non-exploitative, and well-considered procedures are administered fairly, with a fair distribution of costs and potential benefits.

Click or tap here to enter text.

- 3.2. [DETERMINATION] Local context.** Culturally appropriate procedures and an understanding of local context are an important part of protecting subjects. Describe any site-specific cultural issues, customs, beliefs, or values that may affect the research, how it is conducted, or how consent is obtained or documented.

Examples: It would be culturally inappropriate in some international settings for a woman to be directly contacted by a male researcher; instead, the researcher may need to ask a male family member for permission before the woman can be approached. It may be appropriate to obtain permission from community leaders prior to obtaining consent from individual members of a group. In some distinct cultural groups, signing forms may not be the norm.

*This federal site maintains an international list of human research standards and requirements:
<http://www.hhs.gov/ohrp/international/index.html>*

Click or tap here to enter text.

- 3.3. [DETERMINATION] Location-specific laws.** Describe any local laws that may affect the research (especially the research design and consent procedures). The most common examples are laws about:
- **Specimens** – for example, some countries will not allow biospecimens to be taken out of the country.
 - **Age of consent** – laws about when an individual is considered old enough to be able to provide consent vary across states, and countries.

- **Legally authorized representative** – laws about who can serve as a legally authorized representative (and who has priority when more than one person is available) vary across states and countries.
- **Use of healthcare records** – many states have laws that are similar to the federal HIPAA law but that have additional requirements.

Click or tap here to enter text.

3.4. [DETERMINATION] Location specific administrative or ethical requirements. Describe local administrative or ethical requirements that affect the research.

Example: A school district may require researchers to obtain permission from the head district office as well as school principals before approaching teachers or students; a factory in China may allow researchers to interview factory workers but not allow the workers to be paid for their participation.

Click or tap here to enter text.

3.5. [DETERMINATION] If the PI is a student: Does the research involve traveling outside of the U.S.?

- ☐ **No**
- ☐ **Yes** → Confirm by checking the box that (1) you will register with the [UW Office of Global Affairs](#) before traveling; (2) you will notify your advisor when the registration is complete; and (3) you will request a UW Travel Waiver if the research involves travel to the [list of countries](#) requiring a UW Travel Waiver.
- ☐ **Confirmed**

4. RECRUITING AND SCREENING PARTICIPANTS

4.1. [DETERMINATION] Recruiting and screening. Describe how subjects will be identified, recruited, and screened. Include information about: how, when, where, and in what setting. Identify who (by position or role, not name) will approach and recruit subjects, and who will screen them for eligibility.

Note: Per UW Medicine policy, the UW Medicine eCare/MyChart system may not be used for research recruitment purposes. Additionally, researchers may not use UW Medicine's Epic Care Everywhere data for research purposes unless the clinical data is necessary for patient/participant safety activities. This means Care Everywhere data cannot be used for recruitment, data abstraction, or any research activities other than those necessary for patient/participant safety.

We plan to work with the internal medicine hospitalist group (part of our research team) to conduct this study. There will be two lead hospitalists of contact at Montlake, Harborview and Northwest each. The screening hospitalists screen patients who need to be admitted to the hospital as their regular practice. In the meantime, they will screen eligible subjects who meet our inclusion/exclusion criteria. Once eligible subjects are identified, screening hospitalists or admitting hospitalists will explain the rationales of this study and obtain informed consent. This process will be part of the standard admission interview which happens within one hour of admission. The interview happens either in the emergency room or hospital room, depending on whether a hospital room is immediately available. An alternative way of recruitment is that PI: [name] screens eligible subjects and obtains informed consents

4.2. Recruitment materials.

4.2.a. What materials (if any) will be used to recruit and screen subjects?

Examples: talking points for phone or in-person conversations; video or audio presentations; websites; social media messages; written materials such as letters, flyers for posting, brochures, or printed advertisements; questionnaires filled out by potential subjects.

Screening hospitalists will screen eligible subjects when they screen patients who need to be admitted to the hospital.

4.2.b. Upload descriptions of each type of material (or the materials themselves) to **Zipline**. If letters or emails will be sent to any subjects, these should include a statement about how the subject's name and contact information were obtained. No sensitive information about the person (such as a diagnosis of a medical condition) should be included in the letter. The text of these letters and emails must be uploaded to **Zipline** (i.e., a description will not suffice).

HSD encourages researchers to consider uploading descriptions of most recruitment and screening materials instead of the materials themselves. The goal is to provide the researchers with the flexibility to change some information on the materials without submitting a Modification for IRB approval of the changes. Examples:

- *Provide a list of talking points that will be used for phone or in-person conversations instead of a script.*
- *For the description of a flyer, include the information that it will provide the study phone number and the name of a study contact person (without providing the actual phone number or name). This means that a Modification would not be necessary if/when the study phone number or contact person changes. Also, instead of listing the inclusion/exclusion criteria, the description below might state that the flyer will list one or a few of the major inclusion/exclusion criteria.*
- *For the description of a video or a website, include a description of the possible visual elements and a list of the content (e.g., study phone number; study contact person; top three inclusion/exclusion criteria; payment of \$50; study name; UW researcher).*

4.3. **[DETERMINATION]** Relationship with participant population. Do any members of the study team have an existing relationship with the study population(s)?

Example: a study team member may have a dual role with the study population such as being their clinical care provider, teacher, laboratory director or tribal leader in addition to recruiting them for their research.

☒ **No**

☐ **Yes** → Describe the nature of the relationship.

Click or tap here to enter text.

4.4. **Payment to participants.** The IRB must evaluate subject payment for the possibility that it will unduly influence subjects to participate. Refer to the guidance on [Subject Payment](#) when designing subject payment plans. Provide the following information about your plans for paying research subjects in the text box below or note that the information can be found in the consent form.

- The total amount/value of the payment
- Schedule/timing of the payment [i.e., when will subjects receive the payment(s)]
- Purpose of the payment [e.g., reimbursement, compensation, incentive]
- Whether payment will be “pro-rated” so that participants who are unable to complete the research may still receive some part of the payment

The IRB expects the consent process or study information provided to the subjects to include all of the above-listed information about payment, including the number and amount of payments, and especially when subjects can expect to receive payment. One of the most frequent complaints received by HSD is from subjects who expected to receive cash or a check on the day that they completed a study and who were angry or disappointed when payment took 6-8 weeks to reach them.

Researchers should review current UW Financial Management requirements about when Social Security Numbers must be collected, and when research payment must be reported to the UW Tax Office and the IRS: <https://finance.uw.edu/ps/how-pay/research-subjects>.

If your study involves the use of Amazon's Mechanical Turk (MTurk), you must comply with the [UW Procurement Services policy](#) that no UW employee, family member, or student directly involved in the research will participate as a subject. The policy requires adding a qualifying question that asks whether the subject is a UW employee or family member, or UW student who is directly involved in the research. If they answer yes, they must be disqualified from MTurk activities.

none

- 4.5. **[DETERMINATION] Non-monetary compensation.** Describe any non-monetary compensation that will be provided. Example; extra credit for students; a toy for a child.

none

- 4.5.a. If class credit will be offered to students, there must be an alternate way for the students to earn the extra credit without participating in the research. If you will offer class credit, describe the alternative non-research method by which students can earn that same course credit, including who will provide the alternative (e.g., a student subject pool; the course instructor).

Click or tap here to enter text.

- 4.6. **[DETERMINATION] Will data or specimens be accessed or obtained for recruiting and screening procedures prior to enrollment?**

Examples: names and contact information; the information gathered from records that were screened; results of screening questionnaires or screening blood tests; Protected Health Information (PHI) from screening medical records to identify possible subjects.

☐ **No** → Skip the rest of this section; go to [question 5.1](#).

☒ **Yes** → Describe the data and/or specimens (including PHI) and whether it will be retained as part of the study data.

Data will be accessed (but not obtained or recorded) by the screening hospitalists. The screening hospitalists screen patients who need to be admitted to the hospital as their regular practice, so no extra data will be accessed beyond their regular practice.

- 4.7. **Consent for recruiting and screening.** Will consent be obtained for any of the recruiting and screening procedures? (Section [8: Consent of Adults](#) asks about consent for the main study procedures).

"Consent" includes: consent from individuals for their own participation; parental permission; assent from children; consent from a legally authorized representative for adult individuals who are unable to provide consent.

Examples:

- For a study in which names and contact information will be obtained from a registry: the registry should have consent from the registry participants to release their names and contact information to researchers.
- For a study in which possible subjects are identified by screening records: there will be no consent process.
- For a study in which individuals respond to an announcement and call into a study phone line: the study team person talking to the individual may obtain non-written consent to ask eligibility questions over the phone.

☒ **No** → Skip the rest of this section; go to [question 5.1](#).

☐ **Yes** → Describe the consent process.

Click or tap here to enter text.

4.7.a. Documentation of consent. Will a written or verifiable electronic signature from the subject on a consent form be used to document consent for the recruiting and screening procedures?

☐ **No** → Describe the information that will be provided during the consent process and for which procedures.

Click or tap here to enter text.

☐ **Yes, written** → If yes and a written signature will be used to document consent:

- Upload the consent form to **Zipline**.

☐ **Yes, electronic** → If yes and an electronic signature will be used to document consent:

- Upload the consent form to **Zipline**.
- **If the eSignature process or method for recruiting and screening is different than for the main study procedures**, use the questions about electronic consent in Sections 8.3. and 8.4. to differentiate between recruiting/screening and main study electronic consent. **If electronic consent will be used for recruiting/screening but not main study consent**, use 8.3. and 8.4. to describe e-consent and note that it is only for recruiting/screening.

